**TABLE OF CONTENTS**

**1. Project overview/Summary ..... 3**

**2. Introduction ..... 4**

**3. Study Hypothesis ..... 6**

**4. Primary Objective and Secondary Objectives ..... 6**

**5. Research Design ..... 7**

**6. Inclusion/Exclusion Criteria .....10**

**7. Primary and Secondary Measures ..... 11**

**8 Sample Size Calculation ..... 12**

**9. Statistical Analysis ..... 13**

**10. Data Management ..... 13**

**11. Timelines ..... 14**

**12. Trial Supplies ..... 15**

**13. Randomisation procedure and breaking of blinded codes ..... 16**

**14. Assessment of Safety ..... 17**

**15. Publication Strategy ..... 19**

**16. Main References ..... 19**

**17. List of centers and investigators ..... 21**

66 **1. PROJECT OVERVIEW/SUMMARY**

67  
68 **1.1. Background an hypothesis:** Type 2 diabetes (T2DM) is related to reduced pulmonary function. As  
69 experimental studies with *glucagon-like peptide 1* (GLP-1) have shown an increase in pulmonary  
70 surfactant secretion, and the GLP-1 receptor has been found in significant amounts in the lung, it could  
71 be hypothesized that the treatment with liraglutide (a GL-1 agonist) will improve this reduced pulmonary  
72 function

73  
74 **1.2. Aim and specific objectives:** The general aim of this project is to evaluate the effect of short (5-  
75 weeks) incretin-based therapy (liraglutide 1.8 mg once daily) compared to placebo on pulmonary function  
76 in type 2 diabetic patients. Our hypothesis is that liraglutide may ameliorate lung function independently of  
77 weight reduction.

78  
79 The specific objectives are the following:

80  
81 **a.-** To identify changes in the parameters related to respiratory function of 5-week liraglutide 1.8  
82 mg once daily treatment compared to placebo in type 2 diabetic patients. For this purpose  
83 pulmonary volumes, expiratory flows, diffusion lung capacity for carbon monoxide, and exercise  
84 tolerance will be assessed.

85  
86 **b.-** To study the effect on respiratory parameters during sleep of 5-week liraglutide 1.8 mg once  
87 daily treatment compared to placebo in type 2 diabetic patients. For this purpose a previously  
88 validated non-attended respiratory polygraphy will be performed, and the apnea-hypopnea index  
89 (AHI) and the cumulative percentage of time spent with oxygen saturations below 90% (CT90)  
90 will be evaluated.

91  
92 **c.-** To determine whether the mechanism involved in the expected beneficial effect of liraglutide  
93 treatment on lung function could be attributed to their action on surfactant production. For this  
94 purpose changes from basal in serum levels of surfactant A protein, the major surfactant-  
95 associated protein, will be evaluated.

96  
97 **d.-** To establish the effect of 5-week liraglutide 1.8 mg once daily treatment compared to placebo  
98 in type 2 diabetic patients on lung inflammation. For this purpose inflammation markers in  
99 exhaled breath concentrate (nitric oxide, pH, and concentration of nitrites, nitrates and  
100 isoprostane) will be measured.

101

102 **1.3. Study design:** This is a double-blind, randomized, crossover, placebo-controlled study, with two  
103 parallel groups (liraglutide once daily sc vs. placebo sc/once daily) of 18-weeks.

104

105 **1.4. Study periods:** (1) selection, (2) active treatment (7 weeks, 5 of them at 1.8 mg once daily), (3)  
106 wash-out (4 weeks), and (4) alternative treatment (7 weeks).

107

108 **1.5. Sample size:** We have estimated that a number of 60 patients at the end of the study will be  
109 sufficient to test our hypothesis. However, taking into account a drop-out ratio of 20%, the final number of  
110 patients that will be included in the study will be 76 (see details in point 9)

111

112 **1.6. Population to be examined:** Type 2 diabetic patients, treated with metformin ( $\pm$  sulfonylurea) at a  
113 stable dose for at least the previous 3 months, with haemoglobin A1c between 7.0 and 10.0%, BMI  $\geq$  30  
114 Kg/m^2, and no known lung disease.

115

116 **1.7. Participating institutions:** 5 reference Spanish hospitals.

117

118

## 119 **2. INTRODUCTION**

120

### 121 **2.1. Why this work is important?**

122

123 There is growing evidence to suggest an association between type 2 diabetes and impaired pulmonary  
124 function. In this regard, several cross-sectional studies have appeared showing decreased indices of  
125 forced expiration, lung volume and diffusion capacity as the main lung dysfunctions detected in type 2  
126 diabetic populations (*Barrett-Connor et al. Diabetes Care 1996; Davis et al. Diabetes Res Clin Pract*  
127 *2000; Yeh et al. Diabetes Care 2008*). In fact, diabetes is frequently co-morbid with chronic obstructive  
128 pulmonary disease (*Mannino et al. Eur Respir J 2008*), and data from the Atherosclerosis Risk in  
129 Communities Study showed a faster pulmonary function decline in type 2 diabetic patients than in other  
130 participants (*Yeh et al. Diabetes Care 2008*). This is important because the reduction of FEV1 has been  
131 demonstrated an independent cause of mortality in diabetic patients (*Davis et al. Diabetes Care 2004*).

132

133 Interestingly, lung function measures start to decrease several years before the diagnosis of diabetes  
134 (*Davis et al. Diabetes Care 2004*). In this regard we have found that insulin resistance is an independent  
135 determinant of pulmonary function in non-diabetic morbidly obese women (*Lecube et al. Diabetes Metab*  
136 *Res Rev 2010*). In addition, our results suggest that the metabolic pathways related to insulin resistance  
137 are crucial in initiating lung abnormalities in type 2 diabetic patients.

138

139 The reasons for the association between respiratory disease and diabetes are unclear. However, the  
140 relationship between type 2 diabetes and muscle strength, the impairment in lung elastic properties, and  
141 the presence of a low-grade chronic inflammation state are involved. In supporting these findings,  
142 thickening of the alveolar epithelia and pulmonary capillary basal lamina, fibrosis, centrilobular  
143 emphysema, and pulmonary microangiopathy have been detected in autopsies of diabetic patients  
144 (*Nicolaie et al. Rom J Intern Med 2003*). In addition, defects in the bronchiolar surfactant layer, which is  
145 involved in maintaining airway stability and diameter, may also be considered a contributing factor to the  
146 impairment of airway calibre regulation in diabetic patients. When the alveolocapillary barrier is damaged,  
147 surfactant proteins leak into the bloodstream. A recent population-based random sample study has  
148 described how increased circulating levels of surfactant protein A, the major surfactant-associated  
149 protein, were associated with altered glucose tolerance and insulin resistance (*Fernández-Real et al.*  
150 *Diabetes Care 2008*). Therefore, surfactant defects in diabetic individuals may also lead to an increase in  
151 airway resistance and to a reduction in ventilatory patterns as observed in our studies. In addition, as  
152 experimental studies have shown that glucagon-like peptide 1 plays a role in the stimulation of surfactant  
153 production (*Benito et al. Endocrinology 1998; Vara et al. Am J Respir Crit Care Med 2001; Ahrén et al.*  
154 *Horm Metab Res 2004*), its underlying deficit in type 2 diabetes could also enhance the airway resistance  
155 observed in these patients. However, the beneficial effects on pulmonary function using incretin-based  
156 therapies remain to be elucidated.

157

## 158 **2.2. What work has already been done?**

159

160 Our group has recently shown that type 2 diabetes is an independent risk factor for severe nocturnal  
161 hypoxaemia in obese patients (*Lecube et al. PloS One 2009*). In addition, we have provided, for the first  
162 time, evidence that both insulin resistance and type 2 diabetes are risk factors for respiratory function  
163 impairment in morbidly obese women (*Lecube et al. Diabetologia 2010; Lecube et al. Diabetes Metab*  
164 *Res Rev 2010*). The two main abnormalities detected were an obstructive ventilatory pattern and an  
165 increase in residual volume. As a 10% decrease in forced expiratory volume in 1 s (FEV1) has been  
166 associated with a 12% increase in all-cause mortality in diabetic patients (*Davis et al. Diabetes Care*  
167 *2004*), our results have serious implications for patients suffering from obesity and diabetes. Notably, we  
168 have also found a relationship between the degree of blood glucose control (fasting glucose and HbA1c)  
169 and the impairment of pulmonary function tests. In addition, fasting glucose and HbA1c contributed  
170 independently to lung volumes in multiple linear regression analysis. This finding strongly suggests that  
171 metabolic pathways related to hyperglycaemia are the main factor accounting for this impairment and  
172 points to the lung as a new target of long-term diabetic complications. Finally, we have recently provided  
173 first evidence that circulating levels of soluble TNF- $\alpha$  receptors type 1 (sTNF-R1) are related to reduced  
174 lung volumes and airflow limitation in morbidly obese patients, being the main abnormalities a significant  
175 negative correlation between sTNF-R1 and both FEV1 and forced vital capacity (FVC), as well as with the

176 maximum midexpiratory flow (*Lecube et al. Cytokine 2011*). This finding strongly suggests that  
177 inflammatory pathways related to obesity are involved in this impairment and provide a mechanistic  
178 support to previous studies showing an inverse relationship between FEV1 and anthropometric  
179 parameters.

180  
181

### 182 **3. STUDY HYPOTHESIS**

183

184 Our hypothesis is that treatment with an incretin mimetic such as liraglutide may ameliorate lung function  
185 parameters in type 2 diabetics patients, independently of weight reduction. This hypothesis is based on  
186 the following factors:

187

188 **a.-** There is growing evidence to suggest an association between type 2 diabetes and impaired  
189 pulmonary function.

190

191 **b.-** In patients with type 2 diabetes, the incretin effect is severely reduced or absent, contributing  
192 to the reduced lung function parameters observed in type 2 diabetic patients.

193

194 **c.-** GLP-1 stimulates surfactant production in “in vitro” studies and, in consequence, the increase  
195 in surfactant production induced by liraglutide could be the main factor involved in the respiratory  
196 improvement.

197

198

### 199 **4. PRIMARY OBJECTIVE AND SECONDARY OBJECTIVES**

200

201 The main objectives of the project are the following:

202

203 **4.1. Primary objective:** To assess the effect of 5-week liraglutide 1.8 mg once daily treatment compared  
204 to placebo in type 2 diabetic patients on measurements of respiratory function.

205

206 **4.2. Secondary objectives:** To evaluate the effect of 5-week liraglutide 1.8 mg once daily treatment  
207 compared to placebo in type 2 diabetic patients on:

- 208 - the effect on respiratory parameters during sleep,
- 209 - changes from basal in serum levels of surfactant A protein, and
- 210 - inflammation markers in the exhaled air.

211

212

213

214

## 215 **5. RESEARCH DESIGN**

216

### 232 **5.2 Ethic considerations**

233 The trial has been registered in the European Clinical Trial Database (EudraCT number: 2010-023518-  
234 29). Once accepted, the last version of the protocol will be newly submitted to the Investigational Ethics  
235 Committees of all the participating clinical centres. Investigators believe that no major ethical implications  
236 have to be considered in this clinical trial. However, patients diagnosed of severe sleep disorder breathing  
237 will be evaluated with the Pneumology Department in each center. Patients in whom treatment with  
238 continuous positive airway pressure should be considered mandatory will be withdrawn from the clinical  
239 trial. In addition, the trial will follow the Helsinki Declaration as well as the Good Clinical Practice  
240 Guidelines.

241

### 242 **5.3 Study design**

243

244 **5.3.1. Study type:** This is a phase IV double-blind, randomized, crossover, placebo-controlled study, with  
245 two parallel groups (1.8 mg of liraglutide once daily sc vs placebo once daily sc) for 14 weeks.

246

247 **5.3.2. The consent process:** The consent process will begin when a potential research patient is initially  
248 contacted. Prior to any study-related activity, including screening procedures, potential candidates to be  
249 recruited will receive extensive, both oral and written, information about the study, including the risk

250 associated with the study procedures and study-drug. In addition to signing the consent, the patient will  
251 enter the date of the signature on the consent document, to permit verification that consent was actually  
252 obtained before the patient began participation in the study. A copy of the consent document will be  
253 provided to the patient and the original signed consent document will be retained in the study records.

254

255 **5.3.3. Screening phase (population to be examined):** The study will include type 2 diabetic patients,  
256 treated with metformin ( $\pm$  sulfonylurea) at a stable dose for at least the previous 3 months, with HbA1c  
257 between 7.0 and 10.0%, BMI  $\geq$  30 Kg/m^2, and no known lung disease. The patients included in the study  
258 will be recruited from the Endocrinology Departments of all the participating centers and will be followed-  
259 up by the endocrinologists and pneumologists in the investigating teams. The main exclusion criteria  
260 include type 1 diabetes mellitus, treatment with insulin, dipeptidyl peptidase-4 inhibitors and/or  
261 pioglitazone, history of smoking habit, chronic respiratory disease, asthma, cardiovascular disease,  
262 hearth failure, stroke, and/or chest wall disease.

263

264 **5.3.4. Inclusion phase:** After informed consent, the recruited patients will be transferred to Pneumology  
265 Departments where the following examinations will be performed: expiratory flows, pulmonary volumes, 6-  
266 minute walking test, non-attended respiratory polygraphy with oxygen saturation monitoring, inflammatory  
267 markers in exhaled air, and serum surfactant A protein measurement. After these evaluations patients will  
268 be randomly allocated in a 1:1 ratio to one of the two treatment groups.

269

#### 270 **5.3.5. Treatment groups:**

271 **Group A:** (i) 7-week subcutaneous liraglutide treatment once daily, (ii) a 4-week wash-out period,  
272 and (iii) 7-week subcutaneous placebo once daily.

273 **Group B:** (i) 7-week subcutaneous placebo once daily, (ii) a 4-week wash-out period, and (iii) 7-  
274 week subcutaneous liraglutide treatment once daily.

275

276 **5.3.6. Titration schedule:** in order to minimize the loss of weight associated with incretin therapies and to  
277 achieve the optimal dose of liraglutide, active treatment will start at 0.6 mg once daily during the first  
278 week, 1.2 mg once daily during the second week, and 5 weeks at 1.8 mg once daily. Whether a dose of  
279 liraglutide is not well tolerated, it will be reduced to the minimum tolerated dose. Placebo arm will perform  
280 the same scalation that active treated patients.

281

282 **5.3.7. Treatment formulation:** both liraglutide and placebo will be administered subcutaneous using a 3  
283 mL pre-filled pen injector. Regarding liraglutide, one ml of solution will contain 6 mg of the product, so one  
284 pre-filled pen injector will contain 18 mg of liraglutide in 3 mL.

285

[figure not shown]
286 **5.3.8. Sample size:** we have estimated that a number of 76 screened patients at the end of the study will  
287 be able to demonstrate our hypothesis (see below *sample size calculation*).

288  
289 **5.3.9. Baseline treatment:** all type 2 diabetic patients who gave their written informed consent will  
290 continue with metformine ( $\pm$  sulfonyleurea) at the same doses.

291  
292 **5.3.10. Chronogram:** see next page

293  
294 **5.3.11. Visit schedule:** see next page

295  
296  
297  
298  
299  
300  
301  
302  
303

304  
305  
306  
307

	Screening	Basal	Week 2	Week 7	Week 11	Week 13	Week 18
Visit number	-1	0	1	2	3	4	5
Informed Consent	X	-	-	-	-	-	-
Inclusion/exclusion criteria	X	X	X	X	X	X	X
Randomization	-	X	-	-	-	-	-
Physical examination	X	X	X	X	X	X	X
Liraglutide/placebo dispensed	-	X	X	-	X	X	-
Drug accountability	-	-	X	X	-	X	X
Concomitant Medication	-	X	X	X	X	X	X
Expiratory flows	-	X	-	X	X	-	X
Pulmonary volumes	-	X	-	X	X	-	X
6-minute walking test	-	X	-	X	X	-	X
Respiratory polygraphy	-	X	-	X	X	-	X
Nocturnal Oxygen Saturation	-	X	-	X	X	-	X
Serum Surfactant A Protein	-	X	X	X	X	X	X
Inflamm. markers in exhaled air	-	X	X	X	X	X	X
Laboratory	-	X	X	X	X	X	X
Urine pregnancy test (if applicable)	X	-	-	-	X	-	-
Active collection of adverse events	X	X	X	X	X	X	X

308  
309

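### Section 5.3.6 steps a poorly tolerated dose down to the 'minimum' tolerated dose, which read literally skips a tolerated 1.2 mg; 'maximum' was probably meant

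*Combined protocol and SAP*

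**What the plan says.** Section 5.3.6 (Titration schedule) gives two reasons for stepping the dose up: "in order to minimize the loss of weight associated with incretin therapies and to" "achieve the optimal dose of liraglutide, active treatment will start at 0.6 mg once daily". After the first week come "1.2 mg once daily during the second week, and 5 weeks at 1.8 mg once daily". For intolerance there is one rule: if a dose of "liraglutide is not well tolerated, it will be reduced to the minimum tolerated dose". The next sentence has the placebo arm follow "the same scalation that active treated patients".

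The target exposure appears in the same form elsewhere. Section 4.1 (Primary objective): "To assess the effect of 5-week liraglutide 1.8 mg once daily treatment compared" with placebo. Section 1.4 (Study periods): "active treatment (7 weeks, 5 of them at 1.8 mg once daily". The instruction applies at "5 reference Spanish hospitals" (section 1.7).

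Section 7.1 makes FEV1 the primary efficacy measure. In the visit table of section 5.3.11, expiratory flows are measured at baseline and at weeks 7, 11 and 18, so weeks 7 and 18 are the on-treatment measurements at the end of each period.

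**The concern.** A patient reaches 1.8 mg only by passing through 0.6 and 1.2 mg. One who tolerated both and then fails 1.8 mg has two tolerated doses to fall back on. The usual rule is the highest of these; the text names the lowest. The patient would move further from the dose the trial sets out to study than tolerability requires.

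At stake is the dose that down-titrated patients receive, and whether the sites apply the same rule. The visit table schedules no visit between weeks 2 and 7 or between weeks 13 and 18, which is when 1.8 mg is given. Many reductions would therefore be decided between visits, with this sentence as the only written guide. One site could follow it literally and another could assume 'maximum', so the same clinical situation could lead to different doses.

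**Working it through.** The plan states no figure for this point, so there is none to reproduce. The check is a reading of the rule against the dose steps, plus simple arithmetic.

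**Inputs, all from section 5.3.6.** 0.6 mg daily for 1 week, 1.2 mg daily for 1 week, 1.8 mg daily for 5 weeks. The steps add to 1 + 1 + 5 = 7 weeks, which agrees with section 1.4.

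**Step 1: where the word changes the dose.**

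| Dose not tolerated | Doses tolerated before | 'Minimum' gives | 'Maximum' gives |
|---|---|---|---|
| 1.2 mg | 0.6 mg | 0.6 mg | 0.6 mg |
| 1.8 mg | 0.6 and 1.2 mg | 0.6 mg | 1.2 mg |

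The two readings differ only for failure at 1.8 mg.

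**Step 2: daily dose against target.** 0.6 / 1.8 = 33%; 1.2 / 1.8 = 67%.

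**Step 3: cumulative dose for one such patient.** Assume that the reduced dose is kept to the end of the period, and let k be the number of full weeks completed at 1.8 mg.

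- Planned: 7 × (0.6 + 1.2 + 5 × 1.8) = 75.6 mg.
- 'Minimum': 7 × (1.8 + 1.8k + 0.6 × (5 − k)).
- 'Maximum': 7 × (1.8 + 1.8k + 1.2 × (5 − k)).
- Difference: 7 × 0.6 × (5 − k) = 4.2 × (5 − k) mg.

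The two ends of the range are:

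- k = 0 (1.8 mg fails at once): 33.6 mg against 54.6 mg. The difference is 21.0 mg, and 21.0 / 75.6 = 28% of plan.
- k = 4 (1.8 mg stopped after four weeks): 67.2 mg against 71.4 mg. The difference is 4.2 mg, and 4.2 / 75.6 = 6% of plan.

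These totals describe one hypothetical patient. They are not an effect on the trial result.

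**Step 4: is the word corrected or explained elsewhere?** No other readable section defines the term, gives a one-step-down rule or refers to a maximum tolerated dose. The figure after section 5.3.7 and the chronogram announced in section 5.3.10 were not readable, so they could not be checked. Of the two aims in section 5.3.6, the optimal dose points to 1.2 mg. Limiting weight loss could point to 0.6 mg, but the sentence offers it as a reason for starting low and stepping up, whereas the stated trigger for reduction is poor tolerance. The primary objective, set at 1.8 mg, also favours the higher fallback.

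**The case against.** The strongest reply is that this is a language slip. The intended action, stepping down when a dose is not tolerated, is clear, and the specialists following these patients may well not skip a tolerated dose because of one word. That is fair and it limits the weight of the point. It does not remove it, because the sentence is the only reduction rule found and, as written, it gives the wrong dose.

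A second reply is that 'minimum' was deliberate. Section 3 hypothesises an effect on lung function independent of weight reduction, and a lower fallback dose could serve that. The possibility cannot be excluded. But the weight aim is attached to the gradual escalation, not to the tolerability rule, and if 0.6 mg is intended the plan should say so outright.

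A reader might also infer more than the text supports:

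- *That every patient reduced from 1.8 mg has FEV1 measured on 0.6 mg.* This holds only without re-escalation, which section 5.3.6 neither requires nor forbids.
- *That the FEV1 comparison is biased or power is lost.* The documents give no intolerance rate and no dose-response, and no stated sample size or power figure depends on the rule.
- *That the rule covers active drug only, because it names liraglutide.* The trial is double-blind (section 13) and the products look identical (section 12.1), so sites could only apply it to either product.

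**Conclusion.** The point holds as a minor correction. In section 5.3.6 the literal rule sends a patient who tolerated 0.6 and 1.2 mg but fails 1.8 mg to one third of the target dose when two thirds was tolerated. This conflicts with the optimal-dose aim and with the 1.8 mg objective. That 'minimum' stands for 'maximum' is an inference, though a probable one.

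The size is known only per affected patient: 0.6 against 1.2 mg daily and, if the reduced dose is kept, 4.2 to 21.0 mg less over the seven weeks (6% to 28% of plan), with the same daily gap at the week 7 or week 18 FEV1 visit. Patients who tolerate the full titration, or who fail at 1.2 mg, are unaffected. The effect on the FEV1 estimate cannot be quantified and may be small. A comparison of treatments as assigned remains valid under either reading.

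**What to change.** Replace the sentence in section 5.3.6 with, for example: *A patient who cannot tolerate a dose of study drug (liraglutide or placebo) steps down to the highest dose tolerated: 1.2 mg, otherwise 0.6 mg.* Naming both products makes the blinded use explicit. If the sponsor does want 0.6 mg, the sentence should state that dose and the reason.

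The cost is one sentence, with no new visit, measurement or analysis. The downside is possibly somewhat more side effects or weight loss at 1.2 mg than at 0.6 mg, limited because 1.2 mg is used only where it is tolerated. The replacement does not settle re-escalation or intolerance at 0.6 mg; the sponsor may add those, but this correction does not depend on them.

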### 321 **6.2. Exclusion criteria:**

- 322 - type 1 diabetes,
- 323 - treatment with insulin, dipeptidyl peptidase-4 inhibitors, and/or pioglitazone,
- 324 - history of smoking habit,
- 325 - chronic pulmonary obstructive disease,
- 326 - sleep-breathing disorders that require CPAP (continuous positive airway pressure) therapy,
- 327 - asthma,
- 328 - previous bariatric surgery,
- 329 - cardiovascular disease, heart failure, and/or stroke,

- 330 - chest wall diseases,
- 331 - serum creatinine > 1.7 mg/dl,
- 332 - abnormal *liver function test* (ALT/AST levels greater than twice the upper limit of normal),
- 333 - *history of acute or chronic pancreatitis*,
- 334 - *history or family history of medullary carcinoma or the thyroid or MEN 2*,
- 335 - female of child-bearing potential who is pregnant, breast-feeding or intends to become pregnant
- 336 - females of childbearing potential who are not using adequate contraceptive methods (as
- 337 required by local law or practice).

338

339 **6.3. Concomitant therapies:** the next concomitant therapies will be included in the exclusion criteria  
340 because of their effects on pulmonary function or glucose metabolism. Patients enrolled in the study who  
341 initiate any of these concomitant treatments will be also excluded from the study:

- 342 - insulin
- 343 - antidiabetic agents others than metformin or sulfonylureas
- 344 - inhaled bronchodilator drugs or teophillin
- 345 - CPAP (continuous positive airway pressure) therapy
- 346 - oral corticosteroids.

347

348

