417 **10. DATA MANAGEMENT**

418

419 Data management is always the responsibility of the primary investigator. Data management will be  
420 delegated under an agreement of transfer of responsibilities to an external Contract Research  
421 Organisation (CRO). Appropriate measures, including encryption of data files containing person  
422 identifiable data, will be used to ensure confidentiality of patients data, when they are transmitted over  
423 open networks.

424

425 An electronic Case Report Form (eCRF) that accurately represents the protocol of the clinical trial will be  
426 designed and developed by the CRO to collect the specific data.

427

428 The primary investigators of each center will fulfill the sponsor responsibilities detailed in the Spanish  
429 legislation as well as in the Good Clinical Practices of the ICH. To prevent patient confidentiality each  
430 patient will be identified with a unique code, this will be the only identifiable information that will be  
431 recorded in the eCRF. No patient initials will be recorded.

432

433 Monitors designated by the CRO will be responsible for contacting and visiting the investigators for the  
434 purpose of inspecting the facilities and, upon request, inspecting the various records of the clinical study  
435 (eg, case report forms and other pertinent data) to provide that patient confidentiality is respected. The  
436 monitor will also be responsible for verifying the eCRF at regular intervals throughout the study to verify  
437 adherence to the protocol: completeness, accuracy, and consistency of the data; and adherence to local  
438 regulations on the conduct of clinical research.

439

440

441 **11. TIMELINES**

442

443 **Overall study duration:** 24 months

444 **Treatment duration:** 14 weeks

445 **Enrollment period:** 18 months

446 **Anticipated date of first patient visit:** January 18, 2016 (or as soon as contract will be signed)

447 **Anticipated date that first patient enters treatment:** January 25, 2016

448 **Anticipated date that last patient enters trial:** September 26, 2016

449 **Anticipated date that last patient enters treatment:** October 3, 2016

450 **Anticipated date of the final last patient visit:** January 16, 2017

451 **Anticipated date of first manuscript submitted:** May 1, 2017

452 **12. TRIAL SUPPLIES**

453

454 Trial supplies comprise trial products and auxiliary supplies:

455

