595 SAE information must be recorded on an SAE forms and faxed to the Sponsor or designated  
596 organization. Additional information received for a case (follow-up or corrections to the original case)  
597 need to be detailed on a new SAE form and faxed to the Sponsor or designated organization.

598 As a minimum, the investigator should copy Novo Nordisk when expediting SARs or SUSARs,  
599 and should report all SARs related to Novo Nordisk product to the local Novo Nordisk affiliate safety

600 department. The submission to Novo Nordisk must be within day 15 from the investigator's first  
601 knowledge about a valid case.

602

603 **14.5. Pregnancies:** Female patients must be instructed to notify the investigator immediately if they  
604 become pregnant during the trial. The investigator must report any pregnancy in patients who received  
605 Novo Nordisk provided trial product.

606

607 The investigator must follow the pregnancy until the pregnancy outcome and the newborn infant(s) until  
608 the age of 1 month. The investigator must report all information on pregnancy, including AEs in the  
609 patient, the foetus, and newborn infant. All this information must be forwarded to Novo Nordisk.

610

611 When an abnormality is reported in the foetus or newborn infant, information is needed from the male  
612 partner. Informed consent must be obtained prior to this.

613

614 **14.6 Indemnity insurance:** A written assurance indemnity or clinical trial insurance to protect the  
615 institutions from claims of non-negligent harm resulting from the clinical research and to coverage  
616 patients for untoward events will be subscribed by the principal investigator. The amount of  
617 compensations paid should be appropriate to the nature, severity, and persistence of the injury. This  
618 insurance indemnity will be in accordance with Royal decree 223/2004, of 6th February 2004, establishing  
619 the requisites regarding clinical trials.

620

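### The urine pregnancy test is scheduled only at Screening and Week 11, so no test follows period 2 in either group, and Group B's whole liraglutide period has none during or after it

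*Combined protocol and SAP*

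**What the plan says.** **Testing and dispensing.** The visit schedule (5.3.11) has seven visits: Screening, Basal, and Weeks 2, 7, 11, 13 and 18. The row "Urine pregnancy test (if applicable" is marked at Screening and Week 11. The row "Liraglutide/placebo dispensed" is marked at Basal and Weeks 2, 11 and 13.

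**Sequences (5.3.5).** Group A starts with "7-week subcutaneous liraglutide treatment once daily, (ii) a 4-week wash-out period" and then takes placebo for 7 weeks. Group B is "7-week subcutaneous placebo once daily, (ii) a 4-week wash-out period, and (iii) 7" weeks of liraglutide. Allocation is 1:1 (5.3.4) and double-blind.

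**Eligibility.** Section 6.2 excludes a "female of child-bearing potential who is pregnant, breast-feeding or intends to become pregnant", and also women of child-bearing potential without adequate contraception. The row "Inclusion/exclusion criteria" is marked at all seven visits, as is the row for adverse events.

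**Duties once a pregnancy occurs.** Section 14.3 asks that a pregnancy during the study, and its outcome, be recorded and followed up. Section 14.5 tells female patients to notify the investigator at once if they "become pregnant during the trial. The investigator must report any pregnancy in patients who received" the supplied product. The pregnancy is then followed to its outcome and the newborn to 1 month of age.

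**Planned dates (section 11).** The first patient visit is planned for "January 18, 2016 (or as soon as contract will be signed") and first treatment for 25 January 2016. The last patient is to enter the trial on 26 September 2016 and start treatment on 3 October 2016.

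**The concern.** The protocol takes on duties that start only when someone learns of a pregnancy. In period 1, the Week 11 test gives an objective check after exposure. Period 2 has no counterpart, so a woman who conceives then and has not recognised it by Week 18 can complete the trial without the recording, reporting and follow-up in 14.3 and 14.5 being set in motion. For Group B this covers all of the active-drug exposure.

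The two treatment starts are also handled differently. At Week 11 the test and dispensing fall at the same visit. At Basal, when product is first dispensed, there is no test.

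What is at stake is the completeness of safety information on exposed pregnancies. The FEV1 endpoint and its analysis are not affected.

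**Working it through.** No statistical formula applies. The check sets the schedule rows against the treatment sequences. The plan gives no figure of its own on this point to reproduce.

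| | Screening | Basal | Wk 2 | Wk 7 | Wk 11 | Wk 13 | Wk 18 |
|---|---|---|---|---|---|---|---|
| Urine pregnancy test | X | - | - | - | X | - | - |
| Product dispensed | - | X | X | - | X | X | - |
| Criteria re-checked | X | X | X | X | X | X | X |
| Adverse events collected | X | X | X | X | X | X | X |
| Group A | - | liraglutide starts | liraglutide | liraglutide ends | placebo starts | placebo | placebo ends |
| Group B | - | placebo starts | placebo | placebo ends | liraglutide starts | liraglutide | liraglutide ends |

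**Step 1: timeline.** 7 weeks of period 1 + 4 weeks of wash-out + 7 weeks of period 2 = 18 weeks, which matches the last visit. Period 1 is weeks 0 to 7 and period 2 is weeks 11 to 18.

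**Step 2: tests after each period.** Period 1 is followed by one test at Week 11, which is 11 - 7 = 4 weeks after its planned end. Period 2 is followed by none. The last test comes 18 - 11 = 7 weeks before the last visit. In either group, a woman who completes the trial has 7 + 7 = 14 weeks on trial product, of which the last 7 have no later test.

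**Step 3: liraglutide weeks with a later test.**
- Group A: weeks 0 to 7, then Week 11, so 7 of 7.
- Group B: weeks 11 to 18, then no test, so 0 of 7. The Week 11 test falls as exposure begins.

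With 1:1 allocation, about half of the liraglutide periods in women of child-bearing potential would have no later test. That share simply restates the allocation ratio. It does not depend on whether the trial size is read as 60 or 76, both of which appear in sections 1.5, 5.3.8 and 8. The number of women cannot be computed, because no proportion is given.

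**Step 4: first dispensing.** 18 to 25 January is 7 days, and 26 September to 3 October is also 7 days. The planned gap from the Screening test to Basal is therefore about one week, and the available text sets no maximum. From Basal the next scheduled test is 11 weeks later, with visits at Weeks 2 and 7 in between.

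**Step 5: other places a test could be.** The laboratory variables in section 7.3 do not include a pregnancy test. The schedule's laboratory row is not itemised. Sections 6.2, 14.3 and 14.5 schedule no test. The conclusion is limited to the available text, since the consent pages were removed and the chronogram figure is not shown.

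**The case against.** The schedule follows a coherent rule: one test before each treatment period. Section 14.5 sets up detection by patient notification and does not call for a test, so the protocol does what it says. **This stands.** A reader might infer that 5.3.11 contradicts 14.5, but the text does not support that. The duties exist, and the schedule only leaves them less reliably triggered in period 2.

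There are other safeguards. Eligibility, including the pregnancy and contraception criteria, is re-checked at every visit including Week 18, and adverse events are collected each time. **This stands in part.** A reader might infer that a period 2 pregnancy must go undetected, or that a woman dosed from Basal goes 11 weeks without assessment. Neither follows, because history can reveal a pregnancy and the Week 2 and Week 7 visits include a physical examination. But the re-check row names no test, and history finds only what the patient already suspects. At Week 11 the protocol itself re-checks the criteria and tests as well.

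A reader might also infer that only Group B is affected. **That is too strong.** The 14.5 duty covers anyone who received the supplied product, placebo included, so the missing Week 18 test matters in both groups. Only the statement about liraglutide exposure is specific to Group B.

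Nor does 14.5 say that the duty lapses at Week 18. The wording about the trial's duration qualifies the patient's instruction, while the investigator's duty to report carries no end date. What is unclear is whether the patient is expected to notify after her last visit.

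Finally, a one-week gap between Screening and Basal is short. **This stands**, and it makes the Basal point secondary.

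**Conclusion.** The point holds as a gap between the schedule and the duties in 14.3 and 14.5. In the available text, no pregnancy test follows period 2 in either group, and Group B's 7 weeks of liraglutide have no scheduled test during or after them, against 7 of 7 weeks followed by a test in Group A. The Basal point is real but weaker, given the planned 7-day interval.

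The conclusion assumes that visits take place as scheduled (Group A's figure requires attendance at Week 11), that the laboratory row contains no pregnancy test, and that the removed or missing pages do not supply one. The absolute size is unknown and may be small, since the row applies only to women of child-bearing potential and adequate contraception is an entry condition. The change is worth making because it is cheap and makes duties already in the protocol more reliable.

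**What to change.** Reconcile the pregnancy-test row of 5.3.11 with sections 6.2, 14.3 and 14.5:

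1. Mark the existing urine test also at Week 18, or at the end-of-study assessment that 14.3 requires when a patient is removed from treatment. Apply it to both groups, because allocation is blinded and the 14.5 duty covers placebo recipients.
2. Preferably mark it at Basal as well, before dispensing, to match Week 11.
3. State in 14.5 whether the patient's duty to notify continues after the last visit. A test at Week 18 cannot be relied on to find a very recent conception. The interval is for the sponsor to set. The 4-week wash-out is not offered as a basis for it, because nothing in the documents links the two.

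The cost is one or two extra urine tests per woman of child-bearing potential, at visits already scheduled, and one sentence in 14.5. Treatment, endpoints and analysis are unchanged.
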